5.4 Rescue treatment

Subjects may receive prophylaxis if needed. Other rescue treatments may be performed on subjects based upon the PI's decision.

If a subject fails the screening exam due to oral disease such as, but not limited to dental caries and periodontitis, the subject will be appropriately referred to the main MUSoD screening clinic to insure that they will be given an opportunity for full diagnosis and treatment at the school of dentistry or some other appropriate clinic.

6. SAFETY ASSESSMENT

All staff involved in this study will have reviewed the following description of Adverse Events and Adverse Device Effect

6.1. Adverse Event (AE)

An AE is any untoward and unintended medical occurrence in a subject. This definition does not imply that there is a relationship between the AE and the medical device under investigation. An AE which is possibly related, is one that may have been caused by the medical device, or treatment, however there is insufficient information to determine the likelihood of this possibility.

- Possibly related: temporal relationship of the onset of the event, relative to the use/administration of the medical device, is reasonable but the event could have been due to another, equally likely cause.
- Non-related (unlikely): temporal relationship of the onset of the event, relative to the use/administration of the medical device, is not reasonable or another cause can itself explain the occurrence of the event.

Ambiguous cases should be considered as possibly related.

6.2. Adverse Device Effect (ADE)

An ADE is any untoward and unintended response to a medical device. This definition includes any event resulting from insufficiencies or inadequacies in the instructions for use of the medical device or any event that is a result of a user error. This definition also includes treatment- or procedure-related events. ADEs can only occur from the time of medical device use/administration. Here the event is related to the use of the medical device where there is a probable/definite relationship that the event may have been caused by the medical device, or treatment.

- Probably related: temporal relationship of the onset of the event, relative to the use/administration of the medical device, is reasonable and the event is more likely explained by the medical device/treatment than by any other cause.
- Definitely related: temporal relationship of the onset of the event, relative to the use/administration of the medical device, is reasonable and there is no other cause to explain the event.

6.3. Serious Adverse Event (SAE)

An SAE is an AE/ADE occurring during any study phase of the medical device that fulfills one or more of the following criteria that the device:

- Results in death
- Is immediately life-threatening
- Requires in-subject hospitalization or prolongation of existing hospitalization
- Results in persistent or significant disability or incapacity
- Is a congenital abnormality or birth defect
- Is an important medical event that may jeopardize the subject or may require medical intervention to prevent one of the outcomes listed above

If a non-related AE becomes an SAE, i.e. fulfilling one or more of the above criteria, action should be taken.

6.4. Recording of Adverse Events and Adverse Device Effects

At all follow-up visits, adverse changes will be assessed by asking subjects and carrying out the oral safety exam. Subjects may report adverse events at any time of the study. All adverse changes the investigator believes “possibly”, “probably” or “definitely” were caused by the device must be recorded on the case report form as AEs. Time of onset, action taken, outcome and the investigator’s opinion on the relationship of the device to each adverse reaction/change in the oral cavity will also be recorded.

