3. STUDY OBJECTIVES

The objective of this 12-week, parallel-arm, single-blinded, clinical study is to investigate efficacy and safety of a new power toothbrush in comparison with a standard ADA accepted manual brush.

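### Section 6.4 requires case report form entry only for events judged device-caused, which is narrower than the adverse event definition in 6.1

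*Combined protocol and SAP*

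**What the plan says.** Section 3 sets the study's purpose as to "investigate efficacy and safety of a new power toothbrush in comparison with a standard ADA accepted manual brush", so safety relative to the manual brush is a stated aim.

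Section 6.1 defines an AE broadly and adds: "This definition does not imply that there is a relationship between the AE and the medical device under investigation". It describes two relationship classes, possibly related and a second that begins "Non-related (unlikely): temporal relationship of the onset of the event". Section 6.2 adds two more, probably and definitely related, under adverse device effects. Doubtful cases have a default in 6.1: "Ambiguous cases should be considered as possibly related".

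Section 6.3 refers to events that are non-related and not yet serious: "If a non-related AE becomes an SAE, i.e. fulfilling one or more of the above criteria, action should be taken".

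Section 6.4 sets the recording rule: "All adverse changes the investigator believes “possibly”, “probably” or “definitely” were caused by the device must be recorded on the case report form", as AEs. It then asks for onset, action, outcome and the investigator's "opinion on the relationship of the device to each adverse reaction/change in the oral cavity will also be recorded". On collection, subjects are asked about adverse changes at every follow-up visit, and "Subjects may report adverse events at any time of the study".

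**The concern.** The rule for what must be written down is narrower than the definition of what is being collected. Under 6.1 a non-related event is an AE. Under 6.4 it need not be entered as one. Causality then acts as an entry condition instead of an attribute of a recorded event. An event wrongly judged non-related may leave no AE entry for anyone to re-examine.

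Two features of the plan add to this.

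- **Who judges.** Section 6.4 refers to the investigator without saying whether that person is blinded. Section 4.5 gives the principal investigator and the study coordinator access to the randomization key, and the patient schedule has one of them hand out the toothbrush. The judgement that decides entry may therefore be made by someone who knows the arm.
- **What is judged.** Section 2.2 uses the term investigational device for the power brush, and 6.1 speaks of the device under investigation. Section 6.2 says only a medical device, and 5.3 speaks of the toothbrush for any subject. If the device in 6.4 means the power brush, the rule has no clear meaning for a control subject.

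At stake is whether a listing of AEs by arm would be complete and would mean the same thing in both arms.

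**Working it through.** The documents give no AE figure to reproduce, so this is a comparison of text.

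**Step 1. Map the relationship classes to the entry rule in 6.4.**

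- Definitely related (6.2): entry required.
- Probably related (6.2): entry required.
- Possibly related (6.1): entry required. Ambiguous cases are moved here.
- Non-related (6.1): no entry requirement.

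The count is 2 classes in 6.1 + 2 in 6.2 = 4, of which 3 are covered and 4 − 3 = 1 is not. This counts labels. It says nothing about the share of events.

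**Step 2. Look for another route by which a non-related event must be entered as an AE.**

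- *SAE reporting (6.5).* Any SAE goes to the sponsor, and relatedness is determined afterwards. Serious events are covered.
- *Oral cavity examination (4.2.1, Table 2).* Blinded examiners grade each area at every visit and explain any abnormality. Oral findings present at a visit are documented, but the section does not say that they become AEs.
- *Last sentence of 6.4.* It asks for a relationship opinion on oral changes only. It can be read as adding detail to the events in the sentence before it, or as reaching all oral changes. Neither reading covers non-oral events, and neither says that non-related changes are entered as AEs.
- *Discontinuation (5.3) and the two-week visit (4.5).* Gingival trauma attributed to the toothbrush is reported as an AE for any subject. This route also depends on attribution.
- *Questioning at visits, spontaneous reports, the user diary (4.4) and the health-history form.* These are ways for staff to learn of an event. None states an entry rule.

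**Step 3. What remains.** Non-serious events judged clearly non-related have no required AE entry. These are mainly non-oral events, plus oral changes judged non-related.

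**Step 4. Compare with 6.1 and 6.3.** The mismatch with 6.1 is direct: an event that is an AE by definition need not be recorded as one. The mismatch with 6.3 is indirect. Section 6.3 presupposes that a non-related AE is known before it becomes serious, but it sets no recording duty that 6.4 could break.

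**Step 5. Size.** The documents give neither an AE rate nor a share of events judged non-related, so no numerical effect can be derived.

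**The case against.** The strongest reply is that a definition sets no recording duty, so an entry rule narrower than the definition is a choice and not a contradiction. Section 6.4 does not forbid other entries. Oral events are largely captured by the blinded examination whatever their cause, and ambiguous cases default to possibly related. In a toothbrush trial, clearly unrelated, non-serious, non-oral events may be of little interest. Section 7 plans no comparison of AEs by arm; its safety comparison is the abrasion-site count in 7.4. The case report form layout is not visible, and 2.2 binds conduct to operating procedures and good clinical practice, whose content the documents do not give.

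Much of this stands. It confines the point to a small class of events and limits the claim to the text available. It does not remove the point. Leaving entry optional for one class means that the record depends on individual practice, and procedures that cannot be seen cannot be assumed to override an explicit rule.

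A reader might also take the long interval between the 4-week and 12-week visits as a measure of the loss. It is not: it describes visit spacing and would be the same under any wording of 6.4.

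**Conclusion.** The point holds as a gap between the recording rule and the AE definition. Followed as written, 6.4 lets a causality judgement decide what must enter the AE record, in a trial with comparative safety as an objective. The size is unknown and the scope is narrow, as set out above. The safety endpoint in 4.4 (examiner inspection for tissue damage), the abrasion-site comparison and SAE reporting are unaffected.

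Three stronger readings are tempting, and the documents do not support them.

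- *The safety comparison between arms is biased.* The planned comparison does not use the AE record, and no difference in attribution between arms has been shown.
- *Causality is judged unblinded.* This is possible, because the principal investigator can see the key, but 6.4 does not say who makes the judgement.
- *Section 6.4 flatly contradicts 6.3.* That conflict is only indirect.

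The conclusion assumes that no removed page, form or operating procedure requires all AEs to be entered. Confidence is high on the wording gap and low on its practical consequence. It is best classed as a cheap improvement.

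**What to change.** Reword 6.4 so that every AE as defined in 6.1 is recorded on the case report form, in both arms, whatever its relationship. Make relatedness a separate field, completed after the event has been entered, and word it as relatedness to the assigned toothbrush, power or manual.

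This aligns 6.4 with 6.1, provides the record that 6.3 presupposes, and gives the question the same meaning in both arms. It does not by itself make the relatedness opinion blinded, but that opinion would no longer decide whether an event is entered.

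The cost is a wording change and a few more form lines, some for events of little interest. Subjects are already asked about adverse changes at each follow-up visit, so no visit or examination is added.

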6.5. Reporting of Serious Adverse Events

If any SAE occurs, the PI or other personnel is responsible to inform the sponsor within 24 hours after they become aware of the event. The PI also will also inform the IRB committee of SAEs. The PI and sponsor will investigate the event and determined if it is related to the device. If it is a device-related, a report will be issued to the regulatory authority.

7. STATISTICAL ANALYSIS

Each of the two research groups' patients will be assessed clinically at four time points (Baseline, 2 weeks, 4 weeks and 12 weeks). These measures will be compared against one another and over time using a between-within factors repeated measures ANOVA.

Further evaluation of interproximal and marginal scores will also be evaluated with a post hoc analysis.

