4.3. Primary endpoint

The primary endpoint of this study is reduction of gingivitis (change from baseline) as measured by BOP and MGI at baseline, and again at 12-week visits.

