4.4. Secondary endpoints

The following indices and parameters are secondary endpoints.

- Reduction of BOP and MGI at two-week, four-week visits from the baseline
- Reduction of PPD at 2-week, 4-week and 12-week visits from the baseline
- Reduction in plaque by measuring PI at 2-week, 4-week and 12-week visits as well as after a single use
- Safety of the product: clinical examiners inspect for any hard or soft tissue damage
- Patient reported outcomes from an exit survey and user diary

[figure not shown]
CONFIDENTIAL

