4.5. Study procedure

The study to be conducted will be single-blinded, randomized controlled, parallel design. The study population will consist of Seventy-two (72) male and female subjects conforming to the following admission criteria. The subjects meeting the admission criteria with an anticipation of 40% dropout rate will be stratified into two groups balanced for MGI, BOP, PI, and gender using screening data. In this single-blind design, product assignment will be randomized after screening, and only the PI and the Study coordinator will have access to the randomization key.

One group will be assigned to a new power toothbrush while the control group will be assigned an ADA approved manual toothbrush. The study involves a 12-week home use of the respective toothbrushes. Both groups will refrain from the regular use of mouthwash and any interdental device, such as floss, floss picks, toothpicks, water flossing device or interdental brush, during the length of the study. Written instructions on brushing and professional brushing demonstration will be provided at the outset of the study and each participant from both test and control groups will also receive a 2-minute timer to help them monitor their brushing time. Before each visit, subjects are expected to have at least 7 hours, but no more than 12 hours of accumulated, non-brushed, undisturbed plaque/debris.

The study includes four or five visits – screening, baseline, 2-week follow-up, 4-week follow-up and 12-week follow-up. Schematic 1 summarizes the study procedure and visits and Table 2 details procedures in this study. The Screening and the baseline visit may happen on the same day.

Schematic 1. Study and visit procedures

CONFIDENTIAL

CONFIDENTIAL

Visit 2: Baseline
(continued)

A

Use brush per instruction

PI examination after
brushing

Single use
result

Schedule next visit

Pre visit

7 – 12 hours of plaque
accumulation

Visit 3: Follow-up visit
at 2 weeks

Oral examination for tissue abrasion and MGI
by calibrated examiners

Periodontal probing for BOP and PPD
by calibrated examiners

Oral examination for PI
By calibrated examiners

Schedule next visit

Pre visit

7 – 12 hours of plaque
accumulation

Visit 4: Follow-up visit
at 4 weeks

[figure not shown]
Oral examination for tissue abrasion and MGI
by calibrated examiners

Periodontal probing for BOP and PPD
by calibrated examiners

Oral examination for PI
by calibrated examiner

Schedule next visit

A

CONFIDENTIAL

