7.1. Sample size

Assuming an alpha/p-value of 0.05, and a power of 0.95, the minimum number of subjects needed (after all drop-outs have been removed) is 44. Due to the length of the study and multiple visits required within the length of the study, the potential for moderately high drop-out rates is set at 40%. 72 subjects will be initially enrolled; 36 will be assigned to the power toothbrush group, and 36 will be assigned to the manual toothbrush group.

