7.3. Significance level

Unless stated otherwise, significance level is 0.05. A p-value may be complemented by confidence interval.

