7.4. Method

Reductions in gingivitis – BOP, MGI and PPD – and plaque – PI from baseline scores after 2 weeks, 4 weeks and 12 weeks of use will be evaluated. For each subject, mean score of each index will be calculated as well as reductions from baseline at three time points. Additionally, numbers of abrasion sites found will be compared.

Assuming evaluated scores for the test and control groups are denoted U_{Test} and U_{Control} , respectively, the null hypothesis will be tested.

$$H_0: U_{\text{Test}} - U_{\text{Control}} = 0$$

$$H_1: U_{\text{Test}} - U_{\text{Control}} \neq 0$$

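### The only named test, a repeated measures ANOVA over four visits including baseline, is not tied to the 12-week primary endpoint and has no baseline covariate; a baseline-adjusted 12-week contrast needs no new data.

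*Combined protocol and SAP*

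**What the plan says.** - **Endpoint.** Section 4.3 defines the primary endpoint as "reduction of gingivitis (change from baseline) as measured by BOP and MGI at baseline, and again at 12-week visits". Section 4.4 lists "Reduction of BOP and MGI at two-week, four-week visits from the baseline" among the secondary endpoints, so weeks 2 and 4 are not primary.
- **Test.** Section 7 has both groups assessed at baseline and weeks 2, 4 and 12, and continues: "These measures will be compared against one another and over time using a between-within factors repeated measures ANOVA". No other test is named in the document.
- **Derived variables.** Section 7.4 adds: "For each subject, mean score of each index will be calculated as well as reductions from baseline at three time points". It then gives a two-sided null of no difference between test and control on the evaluated scores, without saying which index, visit or test applies.
- **Interval.** Section 7.3 makes interval estimation optional: "A p-value may be complemented by confidence interval".
- **Baseline information.** Section 4.5 has subjects "stratified into two groups balanced for MGI, BOP, PI, and gender using screening data". Under Visit 2 in the same section, full-mouth MGI and BOP are scored before the brush is handed out. Section 7.2 only tabulates the baseline indices by group. No model contains them.
- **Dropout.** Section 7.1 expects 40% dropout and counts 44 subjects once dropouts are removed. No analysis set or missing-data rule is given.

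**The concern.** A statistician following Section 7 could report the group F-test, the group-by-time F-test or a 12-week change-score test as the primary result. These answer different questions and can disagree. The group term dilutes any effect with a visit that precedes treatment. The interaction asks whether the group difference varies anywhere across four visits. If either is read as primary, the trial can claim success on a difference that has gone by week 12, or miss one that is present then.

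There is also a loss of precision. Baseline enters only by subtraction, although each index is measured at baseline and could serve as a covariate.

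Finally, a classical repeated measures ANOVA by default drops any subject who misses a visit. That is a property of the method and not a stated rule of this plan, but with 40% dropout expected the plan should not leave the choice to software.

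**Working it through.** **The plan's own figure.** The 44 evaluable subjects (alpha 0.05, power 0.95) cannot be reproduced, because no effect size, SD, correlation or tested term is stated. With 22 per arm, a two-sided t-test at 95% power implies a difference of about 1.11 SD. A repeated measures interaction calculation gives 44 with f = 0.25, correlation 0.5 and three measurements, but 36 with the four visits of Section 7. Those inputs are guesses, so neither counts as a reproduction. On enrolment, 44/0.6 = 73.3 and 72 × 0.6 = 43.2, close to what is stated.

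**Assumptions for the comparison** (none is in the documents): 22 per arm, SD 1 at every visit, equal correlation ρ between visits of 0.3, 0.5 or 0.7, two-sided alpha 0.05. The effect d is set so that a 12-week ANCOVA has 95% power: d = 1.075, 0.976, 0.805 SD.

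**Formulas** (variance of the between-arm difference):
- ANCOVA at week 12: 2(1 − ρ²)/22 × (1 + 1/40), 41 df
- Change score at week 12: 4(1 − ρ)/22, 42 df
- Group main effect, mean of four visits: 2 × [(1 + 3ρ)/4]/22, 42 df
- Group-by-time: noncentrality (22/2) × Σ(δₜ − δ̄)²/(1 − ρ), 3 and 126 df

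**Worked case: ρ = 0.5, fading effect.** The pattern is d × (0, 1, 0.5, 0), with mean 0.375d and Σ(δₜ − δ̄)² = 0.6875d².
- Interaction: 11 × 0.6875 × 0.976²/0.5 = 14.4, which rejects in 90% of trials.
- Main effect: 0.375 × 0.976 = 0.366, with variance 2 × 0.625/22 = 0.0568, which rejects in 32%.
- Week 12: the true difference is zero, so a 12-week test rejects in about 5%.

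**Rejection rates (%) at ρ = 0.3/0.5/0.7:**

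| Effect at baseline, weeks 2, 4, 12 (× d) | 12-week ANCOVA | 12-week change score | Interaction | Group main effect |
|---|---|---|---|---|
| Fading: 0, 1, 0.5, 0 | 5 | 5 | 84/90/93 | 47/32/20 |
| Equal steps: 0, 1/3, 2/3, 1 | 95 | 84/89/92 | 75/82/87 | 71/52/32 |
| Immediate: 0, 1, 1, 1 | 95 | 84/89/92 | 88/92/95 | 97/85/60 |

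**Precision.** Apart from 1 df, the variance ratio of the adjusted to the change-score comparison is (1 − ρ²)/[2(1 − ρ)] = (1 + ρ)/2 = 0.65/0.75/0.85. So 44 subjects on change scores are matched by 44 × (1 + ρ)/2 = 28.6/33.0/37.4 with adjustment. If the baseline SD is k times the 12-week SD, the ratio is (1 − ρ²)/(1 + k² − 2ρk). For k from 0.8 to 1.25 it runs from 0.50 to 0.98. It cannot exceed 1, because denominator minus numerator equals (k − ρ)².

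**The recommended model under dropout.** This was simulated with 1,500 runs per cell, 36 per arm, unstructured covariance estimated, and 14 and 15 random dropouts in the two arms, leaving 43 completers and about 62 of 72 with a post-baseline visit.
- Mixed model power: 95.5/96.3/94.0% (equal steps) and 95.1/94.8/95.5% (immediate).
- Completer ANCOVA power: 94.3/94.9/91.8% and 94.3/93.5/93.1%.
- Mixed model rejection with no effect at any visit: 5.0/4.6/4.0%; in the fading pattern, 5.5%.

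**The case against.** The strongest reply is that Sections 4.3 and 7.4 together already point to a between-arm comparison of 12-week reductions, so baseline is handled by subtraction and only covariate adjustment is missing. On that reading a single sentence would do: name the 12-week-minus-baseline group contrast within the planned ANOVA. Under the assumptions above, that contrast (pooled error, 126 df) has 85/89/93% power in the equal-steps and immediate patterns, and no true difference to detect in the fading pattern. This is fair. Such a sentence would remove the more serious risk, but the plan does not contain it, and adjustment would still gain precision at no cost.

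Other points stand as limits on size:
- Fixing ANCOVA at 95% is a choice, since Section 7.1 attaches its 95% to no test. Calibrated to the change score instead, ANCOVA would have 97 to 99%. The table shows relative efficiency and does not prove that the plan is underpowered.
- Power loss is not universal. With an immediate effect, the main effect at ρ = 0.3 exceeds ANCOVA (97 against 95%), the interaction ties with it at ρ = 0.7, and the interaction beats the unadjusted change score throughout.
- Eligibility limits on MGI and BOP (Section 5.1) could narrow the baseline spread. At ρ = 0.5 with k of 0.5 to 0.7, the variance ratio is 0.95 to 1.00, so almost nothing is gained.
- The mixed model's advantage over completer ANCOVA is about 1 to 2 points, against a simulation standard error of about 0.6 points per cell (√(0.95 × 0.05/1,500)). Dropout was simulated as random only, so nothing is shown about bias.

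**Conclusion.** The concern holds and should be fixed. The missing link between test and endpoint is visible in Sections 4.3, 7 and 7.4 and rests on no assumption. Its possible consequence is large: with an effect that fades by week 12, an F-test from the named ANOVA would be significant in 20 to 93% of trials, depending on term and correlation, where a 12-week test would be significant in about 5%. The missing covariate adjustment is a matter of efficiency and does not make the analysis invalid. Its size depends on the unstated correlation and SDs: with equal SDs and ρ of 0.3 to 0.7 it is a variance reduction of 15 to 35%, falling to nearly nothing if the baseline SD is much smaller than the 12-week SD, and it costs no more than 1 df. The missing analysis set makes the point more pressing at 40% dropout but is not its core.

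**What to change.** In Sections 7 and 7.4, name as the primary analysis, for each of BOP and MGI, the between-arm difference at week 12 with its 95% confidence interval, from a mixed model for repeated measures on weeks 2, 4 and 12:
- Terms: arm, visit, arm-by-visit, baseline value of that index, baseline-by-visit, and gender, with unstructured covariance.
- Population: all randomised subjects with at least one post-baseline visit, under a stated missing-at-random assumption. Report how many randomised subjects this leaves out.
- Covariates kept few: omit the screening scores, which largely duplicate baseline, and any examiner term.

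A 12-week ANCOVA on baseline and gender with a stated missing-data method is an acceptable alternative; the power figures do not strongly favour one over the other. Keep the planned ANOVA as a supportive analysis. Whether both indices or either one must succeed is a separate decision that this change does not settle.

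The cost is SAP wording and slightly more programming. No new data, visits or subjects are needed.

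### Section 7 names a repeated measures ANOVA over four visits but does not say how sphericity is handled or which error term tests the week-12 change

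*Combined protocol and SAP*

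**What the plan says.** Section 7 has both groups "assessed clinically at four time points (Baseline, 2 weeks, 4 weeks and 12 weeks") and continues: "These measures will be compared against one another and over time using a between-within factors repeated measures ANOVA". No other inferential method is named in the documents.

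Section 4.3 defines the primary endpoint as "reduction of gingivitis (change from baseline) as measured by BOP and MGI at baseline, and again at 12-week visits". Changes at weeks 2 and 4 are secondary (section 4.4).

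Section 7.4 adds: "For each subject, mean score of each index will be calculated as well as reductions from baseline at three time points". It then sets a two-sided null of no difference between test and control scores. It names no test for that null, and does not say whether the scores compared are visit means or changes.

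Section 7.3 fixes the level: "Unless stated otherwise, significance level is 0.05".

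The documents do not mention sphericity, an epsilon correction, a multivariate test, a covariance structure, or the error term for a single-visit contrast.

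**The concern.** A univariate between-within ANOVA uses one pooled within-subject mean square for every within-subject comparison. The visit and group-by-visit F tests hold their level only if all between-visit differences have the same variance. Here the gaps are 2, 2 and 8 weeks. Baseline also precedes use of the assigned brush, while the other three visits follow it. Scores close in time may well correlate more strongly than scores 12 weeks apart.

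If so, the pooled mean square averages short and long intervals. It is then too small for the longest interval, which is the primary one, and too large for the short ones, which are secondary. At stake are the 5% level of the primary comparison and the power of the early comparisons. Because the plan does not settle the error term, it could be chosen after the data are seen.

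**Working it through.** **Inputs from the documents.** Four visits at weeks 0, 2, 4 and 12 (section 7); two-sided 0.05 (sections 7.3 and 7.4); "a power of 0.95, the minimum number of subjects needed (after all drop-outs have been removed) is 44" (section 7.1), so 22 per arm.

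**The plan's own figures.** The documents state no p-value, epsilon or covariance to reproduce. The enrolment figure is close: 44/(1 − 0.40) = 73.3, or 74 for equal arms, against 72 stated (72 × 0.6 = 43.2 completers). That gap does not matter here. The 44 cannot be derived, because no effect size or SD is given.

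**Assumed inputs.** Every covariance below is an assumption.

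**Step 1: one case by hand.** Take equal SDs of 1 and a correlation of 0.30^(gap/12), so 0.30 between baseline and week 12. The variance of a difference is 2(1 − r):

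| Pair (weeks) | r | Variance of difference |
|---|---|---|
| 0 and 2 | 0.818 | 0.364 |
| 0 and 4 | 0.669 | 0.661 |
| 0 and 12 | 0.300 | 1.400 |
| 2 and 4 | 0.818 | 0.364 |
| 2 and 12 | 0.367 | 1.267 |
| 4 and 12 | 0.448 | 1.104 |

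The pooled error implies the same variance for all six, namely their mean: 5.160/6 = 0.860. The ratio R of true to assumed variance is:
- week 2: 0.364/0.860 = 0.42
- week 4: 0.661/0.860 = 0.77
- week 12: 1.400/0.860 = 1.63

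The pooled error has 3 × (44 − 2) = 126 degrees of freedom, with critical t of 1.979. The type I error is about 2[1 − Φ(1.979/√R)]. For week 12, 1.979/√1.63 = 1.55, which gives about 0.121. For week 2, 1.979/√0.42 = 3.05, which gives about 0.002.

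**Step 2: simulation with no arm effect.** 40,000 trials per row, 22 per arm. The simulation standard error is about √(0.07 × 0.93/40,000) = 0.001.

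| Assumed covariance | Epsilon | Group-by-visit F, uncorrected | Same, Greenhouse-Geisser | Week 2, pooled error | Week 4, pooled error | Week 12, pooled error | Week 12, own error |
|---|---|---|---|---|---|---|---|
| Compound symmetry, 0.5 | 1.00 | 0.051 | 0.046 | 0.051 | 0.049 | 0.049 | 0.050 |
| Decay to 0.7 at week 12 | 0.59 | 0.078 | 0.049 | 0.001 | 0.019 | 0.146 | 0.050 |
| Decay to 0.5 | 0.62 | 0.073 | 0.048 | 0.002 | 0.022 | 0.135 | 0.048 |
| Decay to 0.3 | 0.67 | 0.071 | 0.048 | 0.003 | 0.027 | 0.123 | 0.048 |
| Decay to 0.1 | 0.76 | 0.066 | 0.048 | 0.008 | 0.037 | 0.104 | 0.051 |
| Random intercept plus decay | 0.88 | 0.057 | 0.047 | 0.021 | 0.038 | 0.086 | 0.049 |
| Random slope, larger variance | 0.77 | 0.063 | 0.048 | 0.015 | 0.024 | 0.125 | 0.050 |
| Weakly correlated baseline, strongly correlated follow-ups | 0.67 | 0.071 | 0.049 | 0.110 | 0.108 | 0.109 | 0.050 |

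The group main effect stayed at 0.047 to 0.052 throughout. With 36 per arm and decay to 0.3, the uncorrected F gave 0.071 and the pooled week-12 contrast 0.127, so a larger sample does not cure it.

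**Step 3: a narrower baseline.** A separate set of runs used decay to 0.15 to 0.58 with the baseline SD equal to, or 0.6 of, the later SD. It gave:
- uncorrected F: 0.066 to 0.073
- Greenhouse-Geisser F: 0.046 to 0.050
- pooled week 2: 0.002 to 0.010
- pooled week 4: 0.021 to 0.032
- pooled week 12: 0.071 to 0.138
- week 12 with its own error: 0.046 to 0.051

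The narrower baseline lowers the week-12 ratio. In the 0.30 case the variance of the week-12 change becomes 0.36 + 1 − 2 × 0.6 × 0.30 = 1.00, the six-pair mean becomes 0.778, and R falls from 1.63 to 1.29.

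**The case against.** The best defence is section 7.4. It computes one reduction per subject and states a two-sided null for the difference between arms. Read as a two-group test of week-12 change, this is a single contrast that needs no sphericity, and it holds 0.05 in every case above. An ANOVA limited to baseline and week 12 would also be free of the assumption, because with two levels epsilon is 1. This stands as a possible reading, but section 7.4 names no test, and the one method section 7 does name covers four visits.

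A reader might go further and infer that unequal visit spacing by itself breaks sphericity. It does not: compound symmetry satisfies sphericity at any spacing, and the documents give no covariance.

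A reader might also infer that all the p-values are too small. Under decay the pooled week-2 and week-4 p-values are too large, and the group main effect is untouched.

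Nor do the entry thresholds clearly add to the problem. Section 5.1 joins the MGI and BOP criteria by and/or, so neither index need be restricted in every subject. A narrower baseline would in any case reduce the week-12 inflation.

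Finally, Greenhouse-Geisser is a routine adjustment and the omnibus inflation is modest. That is fair, and it limits the weight of the point.

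**Conclusion.** The point holds as a gap in specification with a conditional consequence. Sphericity handling and the error term for the week-12 change are not stated. Under assumed correlations that fall with time (0.15 to 0.58 between baseline and week 12, 22 per arm), the uncorrected group-by-visit F runs at about 0.066 to 0.073. A week-12 contrast on the pooled error runs at about 0.07 to 0.14, and the week-2 and week-4 contrasts at about 0.002 to 0.03. If the covariance is close to compound symmetry, or the week-12 change is tested with its own error, there is no inflation.

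The documents therefore do not support saying that the primary analysis is invalid. They do permit two readings of the same plan, one holding 0.05 and one that may not, and the choice should be fixed in advance. This is an inexpensive improvement worth making.

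**What to change.** In sections 7 and 7.4, state that for each primary index the week-12 arm comparison uses its own error term, in one of two ways:
- a two-group comparison of change from baseline, or ANCOVA of the week-12 score on baseline; or
- the week-12 arm contrast from a repeated-measures model with arm, visit and arm-by-visit, an unstructured within-subject covariance, and a small-sample degrees-of-freedom method such as Kenward-Roger.

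Treat the week-2 and week-4 changes the same way. If an omnibus visit or group-by-visit F is reported, give its Greenhouse-Geisser-corrected p-value.

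The cost is SAP wording and a software option. There is a slight loss of nominal power: a change-score test has 44 − 2 = 42 error degrees of freedom where the pooled error has 126. No visit, subject or measurement changes.
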